### 7.2 *Safety Monitoring*

Triheptanoin adverse drug reactions include GI disturbance and weight gain. Monitoring of these and other potential AEs will occur during study visits and telephone calls throughout the study, as needed. Consultation with a dietician will be utilized as needed.

### 7.3 *Efficacy*

Seizure frequency: The number of observable seizures will be recorded once per day, via diary by patient or caregiver

## 8.0 CRITERIA FOR REMOVAL OF SUBJECTS FROM THERAPY OR ASSESSMENT

Subjects may be removed from the study for the following reasons:

1. Occurrence of an adverse event (AE), a collection of unassociated AE, or a pattern of AE which in the judgment of the Medical Monitor, make further participation in the trial an unacceptable risk of harm to the subject
2. An illness that, in the judgment of the Medical Monitor, might place the subject at risk
3. At the request of the subject or PI
4. In the judgment of the PI, an unacceptable number or seriousness of protocol deviations or unreliable behavior on the part of the subject

## 9.0 POTENTIAL RISKS AND POTENTIAL BENEFITS

Triheptanoin has been used clinically for over a decade in human studies and is currently being developed in a number of different diseases. Approximately 130 subjects with various disorders, including 65 FAOD subjects (ranging from neonates to adults), have been treated

|   |  |
|---|--|
| Protocol Number: 2013-NEUR-001
Version: 4.1
23-Mar-2018 |  |
|---|--|

with triheptanoin for periods up to 13 years with evidence of clinical benefit and no significant safety issues reported.

Data from nonclinical and clinical studies to date suggest triheptanoin does not pose any significant safety risks that can be identified at this time. Triheptanoin has been well tolerated in humans with no significant safety issues and toxicology or adverse pharmacology findings were not observed in triheptanoin -treated animals. Studies in animals and humans suggest triheptanoin consumed orally has side effects that are similar to those of orally consumed medium chain triglycerides. The most commonly reported adverse effects are gastrointestinal distress and excessive weight gain at high doses. Both of these issues appear to resolve when subjects consume triheptanoin in small doses mixed with foods throughout the day and when total caloric intake is appropriately managed.

Overall, the risk-benefit ratio of triheptanoin for GLUT1 DS appears to be favorable based on the safety record to date, the efficacy of triheptanoin in animal models of seizure, the mechanism of action of triheptanoin in providing energy and anaplerotic substrates to the brain, and the significant unmet medical need of GLUT1 DS.

## **10.0 DATA COLLECTION AND ADVERSE EXPERIENCE REPORTING**

### *10.1 Clinical Data Collection*

Data to be collected will include demographic features (gender, age, ethnicity and race), GLUT1 DS medical history, prior and concomitant medications and therapies, details of the 3-day diet record and seizure count from the daily patient diary, and results obtained at each office visit (weight, height, vitals, physical examination, and labs). In addition, data will be collected on adverse events. The entire list of variables and explanations can be found in the Data Dictionary.

### *10.2 Data Management*

Data Management will be provided by Cook Children's Health Care System Research Administration Office (CCHCS RAO) and includes forms design, development of an electronic case report form (eCRF), collecting, managing, editing, storing, and reporting on data; as well as, training and access to the data for the study statistician. The eCRF's will be maintained and updated by CCHCS RAO to reflect the changes within the protocol. This database will be converted to a REDCap database at such time as that platform is fully implemented within the CCHCS RAO.

### *10.3 Data Storage*

|   |  |
|---|--|
| Protocol Number: 2013-NEUR-001
Version: 4.1
23-Mar-2018 |  |
|---|--|

Data will be stored in an electronic database created by CCHS RAO. The database will be password protected and identifiable information will be kept in the database. The database will be maintained on CCHCS servers. Only individuals listed as key study personnel approved by the IRB will have direct access to the database. Any written study-related records will be maintained for at least 3 years following the completion of the study; then destroyed using a cross-cut shredder. Electronic study-related records and results will only be kept in aggregate form following completion of the study.

#### *10.4 Procedures to Maintain Confidentiality*

To minimize the chance of harm associated with PHI and identifiable study data collection, all information abstracted from the electronic medical record will be stored in a password-protected database maintained on CCHCS servers by study staff. To maintain confidentiality, all patient identifiers will be removed prior to disclosure; any disclosed data will be for scientific abstract and publication to the medical community. Consent and assent forms will be locked in the research administration office.

#### *10.5 Quality Assurance*

##### 10.5.1 Edit checks and query resolution

Data entered into the eCRF will be subjected to auto-validation (ranges, data checks) and edits on a “real time” basis as well as batch edits. The batch edits will query inconsistent responses, missing forms, missing data, and data anomalies. The Data Manager will review each discrepancy report. Resolved queries will then be incorporated into the database.

##### 10.5.2 Audit trail

An electronic audit trail of all changes is maintained by the system (i.e., by recording the change, name of user making the change, date/time).

##### 10.5.3 Site monitoring

Site monitoring will be completed by a Cook Children’s Health Care System representative on an internal basis. The functions of internal monitoring include the review of timeliness of provision of data, the collection of initial and updated regulatory documents, and frequency of identified and resolved issues.

#### *10.6 Adverse Event Reporting*

##### 10.6.1 Safety monitoring

|   |  |
|---|--|
| Protocol Number: 2013-NEUR-001
Version: 4.1
23-Mar-2018 |  |
|---|--|

Safety monitoring includes the systematic review of clinical laboratory results and measurement data for trends that may impact patient safety. The processing, reviewing, and reporting of adverse experiences and serious AE are also captured.

- A serious adverse event (SAE) is defined as: Death, or immediately life-threatening, or permanently [or significantly] disabling, or requiring hospitalization, or prolongation of hospitalization, or a congenital anomaly. Elective planned hospitalizations, unrelated to either the disease being studied or the study (e.g., for tonsillectomy), will not be considered serious adverse events.
- An unexpected adverse event is one that is not identified in nature, severity or frequency as described in for these AEDs.

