#### 6.4 *Columbia Suicide Severity Rating Scale (C-SSRS)*

The US FDA has recommended the use of the C-CASA as a standardized suicidal rating system for anticonvulsant trials and other centrally acting agents and nonpsychotropic drugs.

The C-SSRS is a suicidality rating scale that is used extensively across primary care, clinical practice, surveillance, research and institutional settings. It is available in 103 languages and maps to the Columbia Classification Algorithm for Suicide Assessment (C-CASA). The C-SSRS was designed to distinguish the domains of suicidal ideation and suicidal behavior using four constructs: severity of ideation, intensity of ideation, behavior, and lethality. Severity of ideation is rated on a 5-point scale with 1 being "wish to be dead", 2 "nonspecific active suicidal thoughts", 3 "suicidal thoughts with methods", 4 "suicidal intent", and 5 "suicidal intent with plan". The intensity of ideation subscale comprises 5 items, each rated on a 5-point scale: frequency, duration, controllability, deterrents, and reason for ideation. The behavior subscale is rated as actual, aborted, and interrupted attempts; preparatory behavior; and nonsuicidal self-injurious behavior. The lethality subscale assesses actual attempts and is

|   |  |
|---|--|
| Protocol Number: 2013-NEUR-001
Version: 4.1
23-Mar-2018 |  |
|---|--|

rated on a 6-point scale. If actual lethality is zero, potential lethality of attempts is rated on a 3-point scale. The C-SSRS has demonstrated good convergent and divergent validity with other multi-informant suicidal ideation and behavior scales. It is highly sensitive and specific for suicidal behavior classifications. Both the ideation and behavior subscales were sensitive to change over time. The intensity of ideation subscale demonstrated moderate to strong internal consistency

The C-SSRS uses different assessment periods, depending on research or clinical need; the lifetime period assesses the worst-point ideation, which research has suggested may be a stronger predictor of subsequent suicide than current ideation. The following versions will be used in this study: (1) baseline, (2) since last visit, (3) pediatric baseline, (4) pediatric since last visit.

Assessments will be administered for subjects ten years of age and older.

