#### 10.6.2 Medical Safety Monitor

All SAEs will be reported per local IRB policy. This study will utilize a medical safety monitor named in the Independent Medical Monitoring Charter. The Medical Safety Monitor will provide the medical coverage needed when serious or unexpected AEs occur.

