#### 10.6.3 Stopping Rules

The Medical Safety Monitor will act in an advisory capacity to monitor the safety of subjects on a routine basis throughout the trial. The drug safety and pharmacovigilance group at Ultragenyx will review SAEs and may provide advice in any determination of whether study enrollment should be paused or if the study should be halted.

Individual subjects who experience any unexpected and possibly, probably, or definitely drug-related SAEs that represent a change in the nature or an increase in frequency of the serious event from their prior medical history will be assessed as to whether the subject will continue on the study.

Should unexpected and possibly, probably, or definitely drug-related SAEs occur, a full clinical evaluation will be performed by the medical safety monitor, the principal investigator, and drug safety and pharmacovigilance group in order to make a decision regarding what actions to take, including whether to recommend stopping the study and informing the IRB.

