#### 10.6.4 Safety Report

Copies of all reports will be stored in the Study File. All SAEs will be reported to the FDA, the CCHCS IRB, and the supporting institution, Ultragenyx, Inc.

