### 11.0 STATISTICAL CONSIDERATIONS

#### 11.1 *Safety Analysis*

Safety data will be reviewed annually or more frequently, as needed, by another physician investigator familiar with the disorder and treatment. For the safety analysis, the numbers (frequency) and incidence rates of AEs and SAEs will be summarized during exposure to triheptanoin throughout the study. The analyses of safety will include all subjects who receive any triheptanoin during the study and provide any post-treatment safety information. All AEs will be coded using the Medical Dictionary for Regulatory Activities (MedDRA). The incidence and frequency of AEs will be summarized by System Organ Class (SOC), Preferred Term (PT), relationship to study drug, and severity. A by-subject listing will be provided for those subjects who experience a SAE, including death, or experience an AE associated with early withdrawal from the study or study drug treatment.

Clinical laboratory data will be summarized by the type of laboratory test. The frequency and percentage of subjects who experience abnormal clinical laboratory results (i.e., outside of reference ranges) and/or clinically significant abnormalities after study drug administration will be presented for each clinical laboratory measurement. For each clinical laboratory measurement, descriptive statistics will be provided for Baseline and all subsequent scheduled visits during which laboratory measurements were obtained. Changes from Baseline to the treatment visits will also be provided. Descriptive statistics of vital signs and concomitant medications will be provided in a similar manner.

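### The SAE definition in 10.6.1 has no medical-judgement limb, so a medically important event outside its six outcomes bypasses SAE reporting and SAE-triggered review

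*Combined protocol and SAP*

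**What the plan says.** The only SAE definition is in 10.6.1: "Death, or immediately life-threatening, or permanently [or significantly] disabling, or requiring hospitalization, or prolongation of hospitalization, or a congenital anomaly". The sentence after it narrows the list by removing planned elective admissions unrelated to the disease or the study. Nothing widens it.

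Several steps are then tied to SAE status:

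- 10.6.2: "All SAEs will be reported per local IRB policy".
- 10.6.3, company review: "The drug safety and pharmacovigilance group at Ultragenyx will review SAEs". This group may advise on pausing enrolment or halting the study.
- 10.6.3, joint evaluation: "Should unexpected and possibly, probably, or definitely drug-related SAEs occur, a full clinical evaluation will be performed by the medical safety monitor", together with the principal investigator and the company group. The outcome may be a recommendation to stop.
- 10.6.4 Safety Report: "All SAEs will be reported to the FDA, the CCHCS IRB, and the supporting institution, Ultragenyx, Inc".
- 11.1: "A by-subject listing will be provided for those subjects who experience a SAE". The same sentence extends the listing to AEs associated with early withdrawal from the study or from study drug.

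Section 6.4 describes what the C-SSRS captures: "The behavior subscale is rated as actual, aborted, and interrupted attempts", along with preparatory behaviour and non-suicidal self-injury. The scale is given from age ten and continues into the extension year. No section says how a positive C-SSRS finding is classified or escalated, and section 11 names no C-SSRS analysis.

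**The concern.** A closed list of outcomes ties seriousness to what happened to the patient administratively or physically, not to how grave the event was. Two attempts of the same medical importance can be classed differently because one subject was admitted and the other was sent home under supervision. The trial administers an instrument that rates such attempts, and 4.2 excludes subjects with past or current suicidal ideation, behaviour or attempts, so the sponsor already treats these events as important.

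At stake is event-triggered escalation. The primary objective is safety, and the study is open-label with up to 50 subjects followed for up to five years. Individual grave events will carry much of the safety information. If such an event is not an SAE, the plan gives no rule that sends it promptly to the FDA, the IRB or the company, or that calls for the joint evaluation.

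**Working it through.** No arithmetic applies, and the plan states no figure to reproduce. The check is to follow one event through every safety step in the protocol.

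**Step 1: the test event.** Take an actual, aborted or interrupted attempt recorded on the C-SSRS that is not immediately life-threatening, causes no permanent or significant disability, and is managed without admission. Compared with the six outcomes in 10.6.1:

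- death: no
- immediately life-threatening: no
- disabling: no
- hospitalization: no
- prolonged hospitalization: no
- congenital anomaly: no

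It is not an SAE.

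**Step 2: is there another way in?** Sections 6.4, 7.1, 7.2, 8.0, 10.6.1 to 10.6.4 and 11.1 and the two schedules of events were read for any medical-judgement limb. None has one. Section 8.0 relies on the Medical Monitor's judgement about AEs, but that decides whether a subject is removed, not whether an event is serious.

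**Step 3: which steps does the event reach?**

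| Step | Section | Trigger | Reached? |
|---|---|---|---|
| SAE reporting to IRB | 10.6.2, 10.6.4 Safety Report | SAE | No |
| SAE reporting to FDA and company | 10.6.4 Safety Report | SAE | No |
| Company pharmacovigilance review | 10.6.3 | SAE | No |
| Assessment of whether the subject continues | 10.6.3 | Unexpected, at least possibly related SAE that departs from the subject's history | No |
| Joint evaluation, including whether to stop | 10.6.3 | Unexpected, at least possibly related SAE | No |
| By-subject listing | 11.1 | SAE, or AE associated with early withdrawal | Only with withdrawal |
| Medical Safety Monitor coverage | 10.6.2 | Serious or unexpected AE | Only if unexpected |
| Monitor's routine advisory oversight | 10.6.3 | None stated | Open to it |
| Physician review of safety data | 11.1 | At least yearly | Yes |
| AE tables by class, term, relationship and severity | 11.1 | Any AE | Yes |
| Removal of the subject | 8.0 | AE judged an unacceptable risk | Possible |

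**Step 4: reading the table.** The first five rows depend wholly on SAE status, and the listing depends on it unless the subject withdraws. The remaining rows catch the event in some form, but none is prompt external reporting and none leads by rule to the joint evaluation. The route through unexpected AEs is uncertain. As the text reads, the definition of unexpected in 10.6.1 refers to AEDs rather than to triheptanoin, and no reference document can be made out.

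Making the event an SAE would open the reporting and company-review rows outright. The two evaluation rows in 10.6.3 would still require it to be unexpected and at least possibly drug-related.

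**The case against.** The strongest reply is that a non-SAE is far from invisible. Section 7.1 has safety events recorded as AEs, 11.1 tabulates them by severity and relationship, and a physician reviews safety data at least yearly. The Medical Safety Monitor has a routine role not confined to SAEs, and the principal investigator's own site collects AEs at the visits. This stands. A reader might infer that such an event escapes all review, or never reaches anyone with a say in pausing the study. The documents do not support that: only the company group's review is stated as limited to SAEs.

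Three other stronger readings also fail.

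- *Any event managed without admission is non-serious.* The life-threatening and disabling outcomes need no admission, and some suicide attempts would meet the first.
- *A marked liver-enzyme rise would be lost in the same way.* Section 10.6.1 calls for systematic review of laboratory results, 11.1 reports abnormal and clinically significant values and changes from baseline, and laboratory values are named in the primary objective. That example is largely covered.
- *The SAE rate is understated by a known amount.* Assuming one to three such subjects among 50 gives 1/50 = 2% to 3/50 = 6%, but nothing in the documents supports those counts. The SAE rate would also be correct under the protocol's own definition, and the overall AE rate would still count the event.

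It can also be said that the local IRB policy and the Independent Medical Monitoring Charter, both cited in 10.6.2, may fill the gap. They were not available. The protocol does not say that either one alters the SAE definition.

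**Conclusion.** The point holds in a limited form. The definition is closed, and some medically important events fall outside it. For those events the plan as written gives no SAE reporting to the FDA, IRB or company, no company SAE review and no SAE-triggered evaluation of whether to stop. There is also no by-subject listing unless the event is associated with early withdrawal. What is lost is prompt escalation, not recording or all oversight.

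No numerical size can be given. The conclusion rests on the protocol text alone and on two assumptions: that an attempt found on the C-SSRS is recorded as an AE, which no section states explicitly, and that the documents not supplied do not widen the definition. The change is worth making because it concerns subject safety in a trial whose primary objective is safety, and because it is small.

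**What to change.** Amend 10.6.1 with one further limb: any other event that the investigator or the Medical Safety Monitor judges to be medically important. Add a sentence, in 10.6.1 or 6.4, that an actual, aborted or interrupted attempt recorded on the C-SSRS is entered as an AE and assessed against the SAE definition, including the new limb. The reporting, review and listing provisions in 10.6.2 to 10.6.4 and 11.1 then apply without rewording. Check the local IRB policy and the monitoring charter at the same time so that all three use the same definition.

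The cost is one clause and one sentence in an amendment, a few more SAE reports and a slightly higher reported SAE rate. If the change is made while the study is running, the report should state the date it took effect, because SAE counts before and after would rest on different definitions.

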### 5.2 Sources of Research Material

#### 5.2.1 Investigational Product

An investigational form of triheptanoin will be utilized as study drug. This form of triheptanoin is a highly purified form intended for oral administration. It is a medium chain triglyceride of three seven-carbon fatty acids whose formula is:

|   |  |
|---|--|
| Protocol Number: 2013-NEUR-001
Version: 4.1
23-Mar-2018 |  |
|---|--|

This investigational form of triheptanoin is being developed by Ultragenyx Pharmaceutical Inc. as a substrate replacement therapy for the treatment of long-chain fatty acid oxidation disorders (LC-FAOD) and GLUT1 DS.

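### Section 10.6.1 ties an unexpected adverse event to *these AEDs* rather than to triheptanoin, and two of the three SAE-related provisions in 10.6.3 depend on that definition

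*Combined protocol and SAP*

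**What the plan says.** Section 10.6.1 of the combined protocol and SAP defines the term as follows: "An unexpected adverse event is one that is not identified in nature, severity or frequency as described in for these AEDs". A source name may have dropped out after the word *in*, and that gap is not counted as an error here. The legible words *for these AEDs* are the point.

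Section 5.2.1 identifies the product under test: "An investigational form of triheptanoin will be utilized as study drug".

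The defined term is then used in two places:

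- Section 10.6.2: "The Medical Safety Monitor will provide the medical coverage needed when serious or unexpected AEs occur".
- Section 10.6.3, twice. The subject-level provision applies to SAEs that are unexpected, at least possibly drug-related, and represent "a change in the nature or an increase in frequency of the serious event from their prior medical history". The study-level provision reads: "Should unexpected and possibly, probably, or definitely drug-related SAEs occur, a full clinical evaluation will be performed by the medical safety monitor", together with the principal investigator and the drug safety group. That evaluation can end in a recommendation to stop the study.

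The opening paragraph of 10.6.3 has a further SAE-related provision without the term: "The drug safety and pharmacovigilance group at Ultragenyx will review SAEs and may provide advice in any determination" of whether to pause enrolment or halt the study.

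**The concern.** Expectedness is judged against the known profile of a product. Here the definition names a drug class that subjects may be taking alongside the study drug, and does not name the study drug. Safety is the primary objective (section 1.1), and expectedness is one of the conditions that sends an SAE to the two formal assessments in 10.6.3. If the definition is followed literally, an event can be sorted into the wrong category in either direction before anyone considers what it means for triheptanoin.

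**Working it through.** No figure in the plan is at issue, so the check is to set the sections side by side.

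**1. Where the term is defined and used.** *Unexpected* occurs four times: once in 10.6.1 as the definition, once in 10.6.2 and twice in 10.6.3. That leaves 4 − 1 = 3 uses that rely on the definition. No other section defines it.

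**2. What AEDs means elsewhere.** The term appears in five sections. Leaving out 10.6.1, the other four are:

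| Section | Role of AEDs |
|---|---|
| 2.1 | Drugs that patients may need for break-through seizures |
| 2.2.1 | Comparison group in a remark on animal efficacy |
| 4.1 | Permitted concomitant treatment |
| 5.4 | Part of standard of care during the study |

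None of the four uses the term as the name of the study drug. Nothing in 10.6 lists drugs to which *these* could refer. Valproic acid is named once, in 4.2, as an excluded concomitant drug.

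**3. Whose adverse effects the protocol describes.** Sections 2.2.2, 7.2 and 9.0 describe those of triheptanoin, chiefly gastrointestinal upset and weight gain, and 2.2.2 cites its Investigator Brochure. No section describes the adverse effects of any AED.

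**4. What a literal reading does.** Take an SAE that is at least possibly drug-related, and ask whether its nature, severity and frequency are already described for triheptanoin and for the AEDs.

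| Described for triheptanoin | Described for the AEDs | Class against triheptanoin | Class as written |
|---|---|---|---|
| No | No | Unexpected | Unexpected |
| No | Yes | Unexpected | Expected |
| Yes | No | Expected | Unexpected |
| Yes | Yes | Expected | Expected |

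The two references disagree in two of the four cases. In the second row the SAE misses the study-level evaluation, and it misses the subject-level assessment even where it departs from the subject's history. In the third row it enters the study-level evaluation without being new for the study drug. The documents give no event rates, so no probability can be attached to any row.

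**5. Which provisions are affected.** Of the three SAE-related provisions in 10.6.3, two carry the condition (subject continuation and full clinical evaluation) and one does not (the manufacturer's SAE review). In 10.6.2 serious events are covered whatever their expectedness, so only coverage of non-serious events turns on the term.

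**6. What works without the term.** Removal on the medical monitor's judgement (8.0), monitor coverage of serious events (10.6.2), the manufacturer's SAE review (10.6.3, first paragraph), reporting of all SAEs (10.6.4, Safety Report) and safety review at least once a year (11.1). The summaries in 11.1 are by system organ class, preferred term, relationship and severity, and expectedness is not among them.

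**The case against.** The best case for leaving the text alone has four parts.

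- *Triheptanoin may itself count as an AED.* Section 2.2.1 compares it with other AEDs, section 6.4 cites a recommendation for anticonvulsant trials, and the secondary objective is seizure frequency. This softens the charge. But the remark in 2.2.1 is one nonclinical aside, the plural *these* does not suit a single product, and 4.1 and 5.4 use AEDs for concomitant treatment.
- *Readers will know what is meant.* The drug-related condition in 10.6.3 does point to the study drug. It settles causality, though. Expectedness is a separate condition and needs its own reference.
- *No harm is shown.* This stands. A literal misreading would have to get past a safety monitor, the investigator and the manufacturer's own safety group. The third row of the table may also be small: the definition covers severity, so a serious gastrointestinal event could still be unexpected against a triheptanoin reference. The Investigator Brochure was not supplied, so this cannot be settled.
- *The charter may define the term.* Section 10.6.2 says: "This study will utilize a medical safety monitor named in the Independent Medical Monitoring Charter". That document was not supplied, so the possibility stays open.

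A reader might also infer that the definition has no reference at all, so that every drug-related SAE would count as unexpected. The documents do not support this. It relies on the gap after *described in*, where a source name may simply have been lost. Restoring a name would still leave a source *for these AEDs*, and that phrase alone is the error.

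**Conclusion.** Wrong as written, and minor. The only definition of an unexpected adverse event names AEDs where the study drug is triheptanoin. It conditions two of the three SAE-related provisions in 10.6.3, and monitor coverage of non-serious events in 10.6.2.

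Two stronger conclusions are tempting and should be resisted. One is that the whole of 10.6.3 rests on the faulty definition. It does not, because the manufacturer's review has no expectedness condition and can lead to advice on pausing or halting, although it is advisory. The other is that SAEs will in practice be missed. The documents show neither the direction nor the frequency of any misclassification.

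Confidence is high about the wording. The effect on actual safety decisions is unknown, since it depends on how the definition is read and on a charter that was not available. The planned analyses are unaffected.

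**What to change.** In 10.6.1, replace *these AEDs* with triheptanoin and name the source, so that expectedness is judged against the current triheptanoin Investigator Brochure, which 2.2.2 already cites. Cross-reference that single definition in 10.6.2 and 10.6.3, and confirm that the Independent Medical Monitoring Charter uses the same one. Leave the stopping provisions themselves as they are.

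The cost is a one-sentence amendment plus cross-references, with no change to data collection, visits, staffing or analysis. The number of SAEs sent to the two assessments could rise or fall.
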